6.0 DATA AND SPECIMEN SUBMISSION

6.1 Data Collection and Submission

6.1.1 Data submission schedule

A Data Submission Schedule (DSS) is available on the Alliance study webpage, within the Case Report Forms section. The Data Submission Schedule is also available on the CTSU site within the study-specific Case Report Forms folder.

6.1.2 Medidata Rave

Medidata Rave is the clinical data management system being used for data collection for this trial/study. Access to the trial in Rave is controlled through the CTEP-IAM system and role assignments.

Requirements to access Rave via iMedidata:

- Active CTEP registration with the credentials necessary to access secure NCI/CTSU IT systems;
- and
- Assigned a Rave role on the LPO or PO roster at the enrolling site of: Rave CRA, Rave Read Only, Rave CRA (LabAdmin), Rave SLA, or Rave Investigator.

Rave role requirements:

- Rave CRA or Rave CRA (Lab Admin) role must have a minimum of an Associate Plus (AP) registration type;
- Rave Investigator role must be registered as a Non-Physician Investigator (NPIVR), or Investigator (IVR); and
- Rave Read Only or Rave SLA role must have at a minimum an Associate (A) registration type.

Refer to <https://ctep.cancer.gov/investigatorResources/default.htm> for registration types and documentation required.

Upon initial site registration approval for the study in the Regulatory application, all persons with Rave roles assigned on the appropriate roster will be sent a study invitation email from iMedidata. No action will be required; each study invitation will be automatically accepted and study access in Rave will be automatically granted. Site staff will not be able to access the study in Rave until all required Medidata and study-specific trainings are completed. Trainings will be in the form of electronic learnings (eLearnings) and can be accessed by clicking on the eLearning link in the *Tasks* pane located in the upper right corner of the iMedidata screen. If an eLearning is required for a study and has not yet been taken, the link to the eLearning will appear under the study name in the *Studies* pane located in the center of the iMedidata screen; once the successful completion

of the eLearning has been recorded, access to the study in Rave will be granted, and a *Rave EDC* link will replace the eLearning link under the study name.

No action will be required by site staff (to activate their account) who have not previously activated their iMedidata/Rave account at the time of initial site registration approval for the study in the Regulatory application. Pending study invitations (previously sent but not accepted or declined by a site user) will be automatically accepted and study access in Rave will be automatically granted for the site user. Account activation instructions are located on the CTSU website in the *Data Management* section under the Data Management Help Topics > Rave resource materials (*Medidata Account Activation and Study Invitation*). Additional information on iMedidata/Rave is available on the CTSU members' website in the *Data Management > Rave* section or by contacting the CTSU Help Desk at [name] or by email at [contact].

6.1.3 Data Quality Portal

The Data Quality Portal (DQP) provides a central location for site staff to manage unanswered queries and form delinquencies, monitor data quality and timeliness, generate reports, and review metrics.

The DQP is located on the CTSU members' website under Data Management. The Rave Home section displays a table providing summary counts of Total Delinquencies and Total Queries. DQP Queries, DQP Delinquent Forms, DQP Form Status and the DQP Reports modules are available to access details and reports of unanswered queries, delinquent forms, forms with current status, and timeliness reports. Site staff should review the DQP modules on a regular basis to manage specified queries and delinquent forms.

The DQP is accessible by site staff who are rostered to a site and have access to the CTSU website. Staff who have Rave study access can access the Rave study data via direct links available in the DQP modules.

CTSU Delinquency Notification emails are sent to primary contacts at sites twice a month. These notifications serve as alerts that queries and/or delinquent forms require site review, providing a summary count of queries and delinquent forms for each Rave study that a site is participating in. Additional site staff can subscribe and unsubscribe to these notifications using the CTSU Report and Information Subscription Portal on the CTSU members' website.

To learn more about DQP use and access, click on the Help Topics button displayed on the Rave Home, DQP Queries, DQP Delinquent Forms, DQP Form Status, and DQP Reports modules.

6.1.4 ICAREdata® Project

Selected sites will be participating in the ICAREdata® project. - The Integrating Clinical Trials and Real-world Endpoints data (ICAREdata) initiative is a program led by the Alliance Data Innovation Lab which is a component of the Alliance for Clinical Trials in Oncology.

The ICAREdata® project aims to expand the ability to achieve clinical research goals by providing new ways to collect data required for clinical trials. Today, virtually all clinical trials data are collected using special forms and computer applications, such as a software known as Medidata Rave. Instead of using these “add on” data collection systems, the ICAREdata project will gather study data directly from the Electronic Health Record (EHR). As with all research data collections, data collected by the ICAREdata project are stored in a secured repository.

Select institutions will be invited to participate and will receive training on the specific ICAREdata® requirements. As with all clinical trials data management, the nature of data collected using the ICAREdata methods will be specific to a particular research protocol, and might include demographic information, diagnosis, laboratory values, physician assessments, and other results, such as adverse event reports. The Data Innovation Lab will manage data collection, working with the IT department at these sites to configure the EHR to deliver mCODE (minimal common oncology data elements) data and other required outcome data in the form of structured ICAREdata questions. Clinicians will provide the study required data by

answering standardized questions or data fields as part of their encounter visit with the subjects. The IT departments will also work to implement the data transfer capability from the site EHR to the Alliance Data Innovation Lab via a secure/tested extraction method.

Investigators and research staff at limited select sites that utilize the EHR research adverse events data collection tool will be asked to complete a brief voluntary survey. The research staff and investigator's email addresses at these predetermined sites will be submitted at the time of Adverse Events data collection tool training. The survey will take approximately 5 minutes to complete. It will solicit feedback on the investigators and study staff experiences including overall staff acceptance, usability, preferences for using the tool to document any adverse events. The plan survey administration timeline is at baseline and then a select period thereafter. Ultimately, the survey will be used to gather general feedback of the usability of the tool across multiple site level stakeholders.

Data will be encrypted at-rest and in-transit using a secure interface with an established authorization protocol handled by the ICAREdata infrastructure. Alliance Data Lab staff will issue a client ID and credentials to participating ICAREdata sites that will be used to authenticate those sites for access to the ICAREdata infrastructure service/extraction method to submit data. The clinical site will be responsible for securely storing these credentials (e.g., installed on a server that an IT administrator manages) such that those staff responsible for submitting data will have the proper access. Data will be stored and maintained in HIPAA compliant data repositories (such as AWS) and access controlled by an identity server with strict management to ensure confidentiality, integrity, and availability of PHI. Strict access controls will be maintained. Only authorized Alliance Data Lab personnel will have access to the data and scope of access will be further controlled based on role and level of need to know.

Participating institutions may email the Alliance Data Innovation Lab at [contact] with any questions.

6.1.5 IRB Termination

Until institutions receive a formal notice from the Alliance regarding termination to patient follow-up, institutions must not close this trial with the IRB of record for the study. Please contact the Alliance Regulatory team at [contact] with any questions.

6.2 Specimen collection and submission

6.2.1 Correlative Science Manual (CSM)

The Alliance A032002 Correlative Science Manual (CSM) contains instructions for specimen collection, processing and shipping. The manual can be found on the BioMS and CTSU websites. Questions regarding the CSM should be addressed to the contacts specified in the manual.

6.2.2 Central Pathology Review

Retrospective central pathology review using patient diagnostic material is required for all patients registered to this study.

6.2.3 A032002 Biobanking

All participating institutions must ask patients for their consent to participate in the biobanking planned for Alliance A032002, although patient participation is optional. For patients who consent to participate (model consent question, "I agree that my samples and related health information may be kept in a biobank for use in future health research"). Biomarker studies will be performed. Rationale and methods for the scientific components of these studies are described in [Section 14.2](#).

6.2.4 Overview of Specimen Requirements

	After registration & prior to C1D1*	6 weeks after registration	3 months after registration	Disease progression**
Mandatory for all patients:				
Diagnostic H & E slides for histopathology review	X			
For patients consented to A032002 biobanking:				
FFPE tumor tissue	X			
Peripheral Whole blood (EDTA tubes)	2 x 10 mL	2 x 10 mL	2 x 10 mL	2 x 10 mL
Urine (EDTA tubes)	X	X	X	X

* Blood and urine samples should be collected before patient receives first dose of study drug, recommend on the same day of registration

** Progression samples may be collected and submitted up to 1 month after progression. Continue peripheral **Whole Blood (EDTA tubes)** for ct-DNA specimen submission if there is early discontinuation of protocol therapy until disease progression

6.3 Digital radiation therapy data submission using Transfer of Images and Data (TRIAD)

Transfer of Images and Data (TRIAD) is the American College of Radiology's (ACR) image exchange application. TRIAD provides sites participating in clinical trials a secure method to transmit images. TRIAD anonymizes and validates the images as they are transferred.

6.3.1 TRIAD Access Requirements

- A valid Cancer Therapy Evaluation Program (CTEP) Identity and Access Management (IAM) (CTEP-IAM) account.
- Registration type of: Associate (A), Associate Plus (AP), Non-Physician Investigator (NPIVR), or Investigator (IVR). Refer to the CTEP Registration Procedures section for instructions on how to request a CTEP-IAM account and complete registration in RCR; and
- TRIAD Site User role on an NCTN or ETCTN roster.

All individuals on the Imaging and Radiation Oncology Core provider roster have access to TRIAD and may submit images for credentialing purposes, or for enrollments to which the provider is linked in OPEN.

6.3.2 TRIAD Installations

To submit images, the individual holding the TRIAD Site User role will need to install the TRIAD application on their workstation. TRIAD installation documentation is available at <https://triadinstall.acr.org/triadclient/>.

This process can be done in parallel to obtaining your CTEP-IAM account and RCR registration.

For questions, contact TRIAD Technical Support staff via email [contact] or [name].

6.3.3 Procedures for Data Submission via TRIAD

See [Section 7.2.1](#) for details regarding data to be submitted via TRIAD for patients receiving radiation therapy.

6.4 Imaging Data Submission Methods

Data must be submitted according to the protocol requirements for ALL patients registered, whether or not assigned treatment is administered, including patients deemed to be ineligible.

DICOM images uploading is preferred to be submitted using TRIAD, however these methodologies are supported:

- a. TRIAD-based (a PC with internet access and TRIAD software installation will be needed)
- b. Web transfer-based (a PC with internet access and a web browser will be needed)
- c. FTP transfer-based (a PC with internet access and any FTP software will be needed)
- d. Mail/CD Shipment-based (only if electronic transfer approaches cannot be achieved)

Questions regarding image submissions can be sent to [contact].

6.4.1 Detailed Steps of Data Submission

Collection of images is required. Alliance A032002 prescribes limited image acquisition requirements, so any imaging acquired is expected to be done per protocol rather than the site's own standard of care. Specifically, PET/CT, CT, MRI and bone scans must be acquired at the following times and subsequently submitted. Supporting documentation must accompany all submissions for this trial. Images will be collected digitally for central archiving and curation. Imaging studies will be collected digitally at the following time points:

1. Baseline – within 42 days before registration
 - a. CT of the chest/abdomen/pelvis
 - i. Intravenous and oral contrast unless contraindicated
 - ii. 5mm of less slice thickness
 - b. Substitutions allowed:
 - i. CT of the chest and MRI of the abdomen/pelvis
 1. Must be diagnostic quality
 2. Intravenous and oral contrast unless contraindicated
 3. 5mm or less slice thickness
 - ii. FDG-PET/CT of the whole body or limited whole body
 1. CT must be of diagnostic quality
 2. Intravenous and oral contrast unless contraindicated
 3. 5mm or less slice thickness
 - c. Bone scan of the whole body
2. Restaging – every 3 months +/- 14 days
 - a. Same imaging as acquired at baseline
 - b. Bone imaging only required if indicative of metastases at baseline or if signs or symptoms develop
3. Progression

4. Confirmatory Follow-up – 12 weeks after evidence of objective response

The complete imaging data set in digital DICOM format will be submitted electronically to the Imaging and Radiation Oncology Core at Ohio (IROC Ohio) within no more than 3 business days upon the image acquisition completeness. BMP files, JPG files, or hard copies (films) are not acceptable. The raw data of the entire study should be saved until the imaging data is accepted by IROC Ohio.

If not using TRIAD, sites need to de-identify the patient data using institutional procedures to remove patient name and medical record number while preserving the Alliance patient ID number (e.g., 112136) and protocol number (e.g., ALLIANCE032002), respectively.

DICOM tag dates and times cannot be altered prior to submission as they are used to put submissions into context regarding patient treatment. Additional changes to DICOM tags prior to submission impede further technical analysis and should be avoided whenever possible.

Imaging data should be submitted electronically to IROC Ohio via TRIAD, Web Transfer or FTP Transfer:

1. TRIAD based data transfer

The standard TRIAD based data transfer approach will be provided separately through IROC efforts via the specific trial e-mail [contact] per the request by participating sites before their first data submission.

2. Web Transfer

(<http://upload.IROCOhio.org> or <https://moveit.imres.med.ohio-state.edu>)

Any PCs with internet access and web browser (e.g., Chrome, Edge, Internet Explorer, Mozilla Firefox) can be used to web transfer DICOM images and other required files to IROC Ohio. The standard Web Transfer information will be provided separately through the specific trial e-mail [contact] per the request by participating sites before their first data submission.

3. FTP Transfer

Any FTP software can be used to initiate access to the secure FTP Server of IROC Ohio. The standard FTP access information will be provided separately through the specific trial e-mail [contact] per the request by participating sites before their first data submission.

4. Mail/CD Shipment

Only if electronic data transfer approaches cannot be achieved, the de-identified images in digital DICOM format can be burned to a CD and mailed to IROC Ohio. Submit only one patient's images per CD, with the patient's Alliance ID number, study type, date of scans, and name of submitting institution.

Submit these data to:

IROC Ohio
 Attn: ALLIANCE A032002
 The Ohio State University
 [name] █
 [name]
 [contact]
 [contact]

Once the imaging data submission is done, send an e-mail to IROC Ohio at the specific trial email [contact] to inform that the study has been submitted from the institution. IROC Ohio will notify site and ALLIANCE A032002 imaging committee within 2 business days of the data receipt, and then, within 3 business days following the data receipt, of the quality check report.

Send any questions or problems about the data submission to IROC Ohio email [contact] or call [contact] for help.

6.5 Submission of Patient Completed Measures

All participating institutions must ask English-speaking patients for their consent to participate in the correlative study planned for Alliance A032002, although patient participation is optional. For patients registered to correlative study A032002-HO1 (model consent question, “I choose to take part in the Quality of Life study and will fill out these forms”) the quality of life evaluations will be performed. For patients who consent to participate the questionnaires will be completed at the time points listed in the table below (quality of life evaluations should continue in patients who have experienced disease progression, it may be mailed or e-mailed to patients who do not have a planned clinic visit at the specified QOL time point).

Please note that PRO-CTCAE is contained in a separate booklet and is required for all patients per the study calendar. The schedule below only pertains to patients who consent to participate in the Quality of Life study.

Patient-completed booklets for this study are to be ordered prior to the pre-registration of any patients (see [Section 4.3.2](#)). These booklets can be downloaded from the CIRB Approved Documents tab on the CTSU website. Booklets must be given to patients to complete and patients should be instructed to return the booklets/responses to site staff (either in person, by mail, by email, or by phone), and site staff will enter patient responses into Rave. At visits in which booklets are to be completed, the booklet should be given to the patient before any discussion of the patient’s health status or test results. Booklet administration schedule is provided below.

Treatment Arm	≤ 21 days prior to treatment	45 days after registration (+/- 14 days)	6 months after registration (+/- 14 days)	12 months after registration (+/- 14 days)	24 months after registration (+/- 14 days)
For patients registered to A032002-HO1, submit patient-completed questionnaires* at the following time points:					
EORTC QLQ-C30	X	X	X	X	X
EORTC QLQ-BLM30	X	X	X	X	X
PROMIS-Fatigue 8a	X	X	X	X	X
EQ-5D-5L	X	X	X	X	X

* Download EORTC QLQ-C30, QLQ-BLM30, PROMIS-Fatigue 8a and EQ-5D-5L questionnaires for IRB submission and review from the ‘CIRB Approved Documents’ tab on the CTSU website. Verbal administration of the measures for visually impaired patients is permitted if the measure and verbal administration of the measure is conducted in a language understandable to the patients.

6.5.1 Patient Language Considerations

The PROMIS-Fatigue 8a, EORTC QLQ-BLM30, EORTC QLQ-C30, and EQ-5D-5L are available in English only.

7.0 TREATMENT PLAN/INTERVENTION

Protocol treatment is to begin ≤ 14 days of registration.

For questions regarding treatment, please see the study contacts page.

Patients must have completed last systemic cancer therapy within 4 weeks prior to the start of protocol treatment.

It is acceptable for individual chemotherapy doses to be delivered \leq a 24-hour (business day) window before and after the protocol-defined date for Day 1 of a new cycle. For example, if the treatment due date is a Friday, the window for treatment includes the preceding Thursday through the following Monday. In addition, patients are permitted to have a new cycle of chemotherapy delayed up to 7 days for major life events (e.g., serious illness in a family member, major holiday, vacation that cannot be rescheduled) without this being considered a protocol violation. Documentation to justify this delay should be provided.

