3.2.7 Prior Treatment

- No prior allogeneic bone marrow transplantation or prior solid organ transplantation.
- No Prior radiotherapy to targetable site or measurable site.
- No chemotherapy or radiotherapy within 4 weeks prior to entering the study or those who have not recovered from adverse events (other than alopecia) due to agents administered more than 4 weeks earlier. However, the following therapies are allowed:
 - Hormone-replacement therapy or oral contraceptives
 - Palliative radiotherapy for bone metastases >2 weeks prior to registration
- No prior treatment with CD137 agonists or immune checkpoint blockade therapies, including anti-CTLA-4, anti-PD-1, and anti-PD-L1 therapeutic antibodies.
- No treatment with systemic immunostimulatory agents (including, but not limited to, interferon and interleukin 2 [IL-2]) within 4 weeks or 5 half-lives of the drug (whichever is longer) prior to initiation of study treatment
- No prior treatment with any other investigational agent within 4 weeks prior to registration.
- No prior treatment with systemic immunostimulatory agents (including, but not limited to, interferon [IFN]- α or interleukin [IL]-2) within 6 weeks prior to registration.
- Any prior systemic therapy is permitted except therapy with PD1/PDL1 inhibitor.
- Patients who have received acute, low dose, systemic immunosuppressant medications (e.g., a one-time dose of dexamethasone for nausea) may be enrolled.
- The use of inhaled corticosteroids and mineralocorticoids (e.g., fludrocortisone) for patients with orthostatic hypotension or adrenocortical insufficiency is allowed.

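### Section 7.0 words the interval since last systemic therapy as a 4-week maximum, which contradicts the 4-week minimum for chemotherapy in Section 3.2.7

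*Combined protocol and SAP*

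**What the plan says.** Section 7.0 (Treatment Plan/Intervention) contains two timing rules that matter here: "Protocol treatment is to begin ≤ 14 days of registration" and "Patients must have completed last systemic cancer therapy within 4 weeks prior to the start of protocol treatment".

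Section 3.2.7 (Prior Treatment) sets these intervals:

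- Chemotherapy: "No chemotherapy or radiotherapy within 4 weeks prior to entering the study".
- Investigational agents: "No prior treatment with any other investigational agent within 4 weeks prior to registration".
- Systemic immunostimulatory agents, in two separate bullets. One bars them "within 4 weeks or 5 half-lives of the drug (whichever is longer) prior to initiation of study treatment". The other ends "interleukin [IL]-2) within 6 weeks prior to registration".

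Otherwise Section 3.2.7 allows any earlier systemic therapy except PD-1/PD-L1 inhibitors, and it gives no upper limit on the time since that therapy.

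Section 3.2.2 admits platinum-refractory patients by two routes: perioperative platinum with relapse inside 12 months, or platinum given for metastatic disease with no time limit. Platinum status is also a stratification factor (Section 4.6.1).

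**The concern.** Both sections define the same kind of window, the 4 weeks before a start point. Section 3.2.7 forbids chemotherapy inside that window. Section 7.0 requires the last systemic therapy to have ended inside it. The start points differ by at most 14 days, and that difference does not create room for both rules.

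Platinum-refractory patients are one of the two populations the trial is built for, and all of them have had chemotherapy. If platinum was their last systemic therapy, almost any interval that satisfies the eligibility section breaks a rule that Section 7.0 states as mandatory. A site that follows Section 7.0 literally could withhold the first dose from an eligible, randomized patient. A site that follows Section 3.2.7 departs from Section 7.0. It cannot escape by relaxing Section 3.2.7, because Section 3.0 says eligibility requirements cannot be waived.

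**Working it through.** The plan gives no figure to reproduce. The check is whether any timing satisfies both sections.

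**Inputs**

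- d = days from last dose of earlier therapy to registration.
- T = days from registration to first protocol dose, 0 to 14 (Section 7.0).
- Gap to first dose: g = d + T.
- 4 weeks = 28 days and 6 weeks = 42 days, in line with the protocol's day-counting convention (a Monday to the next Monday is 7 days).

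**Rules**

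- Section 7.0 as written: d + T ≤ 28.
- Section 3.2.7, chemotherapy (study entry taken as registration) or investigational agent: d ≥ 28.
- Section 3.2.7, immunostimulatory agent, 6-week bullet: d ≥ 42.

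**Chemotherapy or investigational agent**

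From d ≥ 28 and d + T ≤ 28 it follows that T ≤ 28 − d ≤ 0. So T = 0 and d = 28, a single combination. If day 28 itself is barred by Section 3.2.7, then d ≥ 29 and d + T ≥ 29 > 28, so no combination is left.

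The single combination needs day 28 to be inside the window in Section 7.0 and outside it in Section 3.2.7. If day 28 is treated the same way in both, none remains:

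- inside in both: d ≥ 29 against g ≤ 28;
- outside in both: d ≥ 28 against g ≤ 27.

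**Study entry read as first dose (chemotherapy only)**

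The rules become g ≥ 28 and g ≤ 28, so the overlap is still the one value g = 28.

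**Immunostimulatory agent as last cancer therapy (a separate case)**

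With d at its minimum of 42, g runs from 42 + 0 = 42 to 42 + 14 = 56 days. Against a limit of 28, the excess is 42 − 28 = 14 to 56 − 28 = 28 days. No combination satisfies both rules. The other bullet, with its half-life clause, can only lengthen the gap.

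**Section 7.0 read as a minimum**

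The rule becomes d + T ≥ 28. With d ≥ 28 and T ≥ 0 this always holds, so the conflict disappears for every chemotherapy patient who meets Section 3.2.7.

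**A general 4-week minimum placed in Section 7.0 alone**

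For a therapy that Section 3.2.7 does not restrict, d + T ≥ 28 with T ≤ 14 requires d ≥ 28 − 14 = 14. A patient with d from 0 to 13 could be registered but could not start on time. A general minimum would therefore also have to appear in the eligibility section.

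**The case against.** The strongest reply is that the protocol, read as a whole, makes the intent clear. The chemotherapy bullet in Section 3.2.7 goes on to deal with patients who have not recovered from treatment given longer than 4 weeks ago, so it expects such patients. Section 3.2.2 accepts relapse up to 12 months after perioperative platinum and puts no limit on platinum for metastatic disease. A sensible site would take the Section 7.0 sentence as a washout. This stands, and it keeps the practical effect modest. It does not repair the sentence, which says the opposite of what was probably meant, and no other section corrects it.

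Four stronger readings are tempting, and the documents do not support them:

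- **That affected patients become ineligible and drop out of the primary analysis.** The modified intent-to-treat set in Section 13.6 excludes ineligible patients. But Sections 4.4 and 12.5 judge eligibility on the eligibility criteria, and the Section 7.0 sentence is not one of them.
- **That every departure is a protocol violation.** Section 7.0 excuses certain cycle delays from that label, which suggests that timing departures can count. The documents do not classify this one.
- **That a percentage of patients in breach can be given.** The documents do not say how long before registration patients had their last therapy. A share of admissible calendar days would not be a share of patients.
- **That newer non-chemotherapy agents have no washout at all.** This depends on how broadly chemotherapy is read. The protocol uses the word loosely: Section 7.0 says "It is acceptable for individual chemotherapy doses to be delivered" in a trial whose only systemic drug is pembrolizumab, and the chemotherapy bullet needs an exception for "Hormone-replacement therapy or oral contraceptives". The gap is possible but not shown.

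**Conclusion.** The contradiction is real. For a patient whose last systemic therapy was chemotherapy or an investigational agent, one combination of timings satisfies both sections (28 days to registration, same-day start), or none if day 28 is treated alike in both. For an immunostimulatory agent as last cancer therapy there is none. The 6-week figure belongs to that group only; for chemotherapy the minimum is 4 weeks.

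The result rests on reading the Section 7.0 sentence as written and on the 0-to-14-day start. It does not depend on whether study entry means registration or first dose. Patients with no earlier systemic therapy are outside it.

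The sentence is most likely a slip for a minimum of 4 weeks. The consequence is a compliance problem at first dose, chiefly for platinum-refractory patients. Chemotherapy washout is already protected by Section 3.2.7, and eligibility status, analysis set, sample size and power are unaffected. It should be corrected, but it is not a design fault.

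**What to change.** The sponsor should first state which rule it intends.

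**If no additional washout is intended**, replace the Section 7.0 sentence with:

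> Prior systemic cancer therapy must satisfy the minimum intervals in Section 3.2.7, each counted to the time point stated there (study entry, registration or start of study treatment); there is no maximum interval.

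This adds no restriction. Naming the time points matters: without them, the sentence could be read as letting an interval that must be complete at registration run on until the first dose.

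**If a general washout for all systemic cancer therapy is intended**, write instead:

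> Any prior systemic cancer therapy must have ended at least 4 weeks before the first dose of protocol treatment; longer intervals in Section 3.2.7 govern.

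In that case, add the same 4-week minimum before registration to Section 3.2.7, so that nobody is registered who cannot start within 14 days.

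The cost is one sentence in an amendment, or two under the second option. Design, sample size and analysis do not change.
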